**'TOUCH TARGET'**

**[name]  
DOG TRAINING**

**Things you'll need: Treats, Pocket or Pouch, Clicker**

**STEP 1**

- Put your palm in front of your dog's nose
- When he touches your hand with his nose, CLICK, then treat from your pocket. He did touch!
  - If he doesn't touch your hand, get it smelly (like with hotdogs) first.
  - If he still doesn't touch your hand, put a treat under your thumb, with the rest of your palm open.
- After a few (5-10) TOUCHes, move your hand back a few inches.
- Keep moving your hand back a little until your hand is at your side, and your dog has to move to TOUCH.
- Practice, until it's easy for you and your dog!

**STEP 2**

- Next, ask for a TOUCH without any treats nearby.
- When your dog TOUCHes:
  - Show him your empty hand(s)/pocket
  - Give him a treat from someplace else/farther away (for example, the table, etc)
- This teaches your dog to do what you ask without a bribe (a treat). It also teaches him to wait for the reward.
- Practice until this is easy for you and your dog!

**STEP 3 (optional)**

- Once your dog is almost always doing TOUCH without treats, you can say "TOUCH" with the hand signal.

## Assessing an animal-assisted treatment program for adults with aphasia: the Persons with Aphasia Training Dogs (PATD) Program

using the positive reinforcement techniques, not on the performance of the dog. Dogs' behaviors in response to cuing are noted to provide for qualitative assessment of the participant's responsivity to the dog and so that relief (e.g., break for walk or play) may be immediately provided to the dog if signs of stress, fatigue, etc. are observed.

**Statistical Considerations:** Scores from weekly probes will allow for analysis of change in level of 'competence' over time, as determined using the *PPAHE* for that skill. For the purpose of statistical analyses of weekly evaluations, three scores (0= "not ready", 1= "ok", 2= best") will be dichotomized as competent (1 or 2) vs. not competent (0). In addition to the weekly evaluations, at the end of the training period, each participant will receive a summative score on the adapted *PPAHE*. This score may range from 0 to 10. In keeping with our a priori hypothesis that participants will be able to independently cue a dog to perform a minimum of 4 out of 5 obedience behaviors, a score of 5/10 points corresponds with achieving a minimum of a 1 ("ok") on all five targeted obedience behaviors or achieving a 2 ("best") on at least one behavior and 1 on three others. For the primary analysis, the proportion of subjects that successfully completed the training will be quantified with the corresponding two-sided 90% exact binomial confidence interval. For the secondary analysis, (i) the median cumulative score will be computed with the corresponding two-sided 90% distribution-free confidence interval (Hahn & Meeker, 2011) and (ii) the weekly competence scores will be analyzed using the repeated measures logistic regression model. With the total sample size of 20 subjects, the width of the two-sided 90% exact binomial confidence interval is at most 0.38 if the observed proportion of subjects successfully completed the training is 0.5. The interval is narrower if the observed proportion of successes is higher (or lower) than 0.5.

**Expected results:** It is expected that participants will be able to independently cue a dog to perform a minimum of 4 out of 5 obedience behaviors. It is also expected that the median cumulative score will be at least 5, which corresponds with achieving a minimum of a 1 ("ok") on all five targeted obedience behaviors or achieving a 2 ("best") on at least one behavior and 1 on three others.

**Scientific rigor:** To maintain treatment fidelity, all PATD training will be conducted by the PI. PATD training sessions will be digitally video recorded. Control for experimenter bias will be achieved by having skill probes scored via video-recording by one CPDT, and having summative evaluation conducted and scored by a second CPDT. The PI will not be present for the summative evaluations. For the purposes of establishing inter-rater reliability, summative evaluations will be digitally video recorded so that a third CPDT can independently evaluate participant performance. PSPCA participants may work with a different dog each week to accommodate for the fact that the same dog may not be available for training from week to week. All CPDTs will be practitioners of positive reinforcement training, the cuing and shaping techniques for which are relatively standard and are familiar to practitioners of the technique.

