### APPROACH

Accomplishment of the overall objective of this application will be achieved through this small-scale, feasibility study aimed to garner preliminary support for our hypotheses and to provide the foundation for a future, large-scale clinical trial.

**Specific Aim 1: Determine whether PWA, through participation in the PATD program, can learn and implement positive reinforcement techniques to train dogs in basic obedience skills.** *Hypothesis 1:* On program completion, PWA will be competent in using positive reinforcement techniques, to independently cue a dog to complete a minimum of 4 (of 5) trained obedience skills. To test this hypothesis, we will assess program participants using a PI-adapted version of the *Pet Partners® Animal-Handler Evaluation*.

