**Skills Practice:** Participants will not be required to complete all steps for an obedience skill in a single session, and will be encouraged to practice the skill with the dog for at least 3 practice sessions over the course of the week. Practice will be used as a measure of participant compliance. Each participant will be provided with a copy of the lesson plan and, if interested, a video demonstrating the PI performing the target skill with her own dog. Participants will also be provided with a training log to complete after each time they practice over the course of the week. Using a nine-point visual analog scale adapted from the *Assessment of Living with Aphasia* (ALA) (Simmons-Mackie et al., 2014), participants will rate their own and the dog's performance during each practice session (see *PATD Practice Log*, in Appendix). To facilitate responses on the log, participants will practice self-reflection with the PI during training sessions (e.g., "How many times did I have to cue the dog?", "Did I 'click' as soon as the dog did what I asked?").

**Skills Evaluation:** In consultation with a CPDT who is a practitioner of positive reinforcement training, the PI-adapted *Pet Partners® Animal-Handler Evaluation (PPAHE)* will be used to evaluate handler competence, on parameters associated with shaping and timing, on a scale of 0 ("not ready") to 2 ("best") (see blank *PPAHE* in Appendix). Weekly single-skill probes will be conducted by the PI/trainer but will be scored via video-recording by a certified professional dog trainer (CPDT). Summative assessment of all skills will occur twice, within one week of training completion and at a 3-month follow-up. Summative assessments will be completed in person by a CPDT who will also score the weekly formative evaluations via video-recording. To maintain scientific rigor, the CPDT will score probe evaluations via video after the follow-up in person summative evaluation has been completed. As reflected in the adapted *PPAHE*, scores will be based solely on participants' competence

**MossRehab Aphasia Center  
PATD Program**

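### The Aim 1 outcome supports a claim about handler competence but not the dog-completion part of Hypothesis 1, so the wording and the score should be aligned

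*Combined protocol and SAP*

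**What the plan says.** Under Approach, Specific Aim 1 asks whether people with aphasia "can learn and implement positive reinforcement techniques to train dogs in basic obedience skills". Hypothesis 1 is that "PWA will be competent in using positive reinforcement techniques, to independently cue a dog to complete a minimum of 4 (of 5) trained obedience skills". The Aim 1 Expected results paragraph repeats the second part: "participants will be able to independently cue a dog to perform a minimum of 4 out of 5 obedience behaviors".

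The adapted PPAHE is the only instrument named for testing this hypothesis. Skills Evaluation says that it "will be used to evaluate handler competence, on parameters associated with shaping and timing", on a 0 to 2 scale, and that "scores will be based solely on participants' competence" in "using the positive reinforcement techniques, not on the performance of the dog". What the dogs do is recorded separately: their behaviors "in response to cuing are noted to provide for qualitative assessment", namely of how the participant responds to the dog, and so that the dog can be given relief if it shows stress or fatigue.

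The Aim 1 Statistical Considerations tie the 4-of-5 hypothesis to a summative PPAHE total of 5 out of 10. The primary analysis is the proportion of participants who successfully completed the training, with a two-sided 90% exact binomial interval. The secondary analyses are the median total score and a repeated-measures logistic model of weekly competence. Statistical Design and Power gives the same analyses.

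**The concern.** A reader who meets the phrase "to independently cue a dog to complete a minimum of 4 (of 5) trained obedience skills" will take it that the dogs carried out the skills. The number reported under that sentence will be a handler-technique score. The two can part in either direction:

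- Under Scientific rigor, shelter participants may have a different dog each week, so sound technique may meet a dog that has not learned the skill.
- The dog exclusions under Dog-training (in the section on risks) cover bites, reactivity and resource guarding. They do not cover prior training, so a family dog may sit on cue whatever the handler's technique.

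This is the primary claim of Aim 1. The study is meant as the foundation for a large trial, and its results are to be posted publicly. What the Aim 1 proportion is a proportion of should be clear before it is quoted.

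**Working it through.** **1. Claim and measurement side by side.**

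| Element | Subject | Criterion | Counted in an analysis? |
|---|---|---|---|
| Aim 1 | participant | learns and applies the techniques | yes, by PPAHE |
| Hypothesis 1, first part | participant | competent in technique | yes, by PPAHE |
| Hypothesis 1, second part; Expected results | participant and dog | dog completes or performs at least 4 of 5 skills on cue | no |
| Dog response at evaluation | dog | noted | no, qualitative and welfare use only |

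Dog performance also enters the training rule in Skills Training, where five successful trials by participant and dog are needed to move to the next step. It does not enter the summative score, the primary proportion or either secondary analysis.

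**2. Where the plan equates the two.** Statistical Considerations passes from the 4-of-5 wording straight to a handler total of 5/10. Preliminary Data describes the four pilot participants as able to cue four of five skills at a handler level of 1 or more. Neither place reports dog performance separately from handler score, so the equivalence is asserted and not shown.

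**3. The 5/10 benchmark for handler technique alone.** The plan's two examples reproduce: 1+1+1+1+1 = 5, and 2+1+1+1+0 = 5. They are not the only routes to 5, and 5 is not the lowest total with four competent skills. Five skills scored 0, 1 or 2 give 3^5 = 243 patterns:

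| Rule | Patterns |
|---|---|
| Total of 5 or more | 147 |
| Score of 1 or more on at least 4 skills | 112 |
| Both | 107 |
| Total of 5 or more, fewer than 4 competent skills | 147 − 107 = 40 |
| At least 4 competent skills, total below 5 | 112 − 107 = 5 |

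The 40 are the orderings of 2,2,1,0,0 and 2,2,2,0,0 (three competent skills). The 5 are the orderings of 1,1,1,1,0 (total 4). These are counts of patterns, not probabilities.

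**4. How far handler and dog figures could differ.** The documents give no rate at which a dog performs a skill for a handler scoring 1 or more. Call it q, vary it, and assume skills are independent.

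- Handler competent on all five: P(dog performs at least 4) = q^5 + 5q^4(1 − q). At q = 0.8 this is 0.328 + 0.410 = 0.737 (unrounded terms).
- Handler competent on exactly four, counting only those four: q^4. At q = 0.8 this is 0.41.

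| q | Competent on five | Competent on four |
|---|---|---|
| 0.95 | 0.98 | 0.81 |
| 0.9 | 0.92 | 0.66 |
| 0.8 | 0.74 | 0.41 |
| 0.7 | 0.53 | 0.24 |
| 0.5 | 0.19 | 0.06 |

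If all 20 participants were competent on all five skills, the handler proportion would be 20/20. At q = 0.8 the expected number whose dog performed at least four would be 20 × 0.737 = 14.7. The two proportions agree only when q is close to 1.

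**5. The plan's stated precision.** The only figure attached to the Aim 1 primary analysis is an interval width of at most 0.38 at an observed proportion of 0.5. The Clopper-Pearson 90% interval for 10/20 is 0.302 to 0.698, a width of 0.396. That is a separate matter, and this point does not depend on it.

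**The case against.** The strongest defence is that handler-only scoring is deliberate and right. Aim 1 and the first part of Hypothesis 1 are about the participant's competence, which the PPAHE measures. Counting what the dog does would mix participant learning with the dog's history, and changing shelter dogs would make that worse. The plan also discloses that it reads the 4-of-5 hypothesis through handler scores, and it sets no test or success threshold for the Aim 1 proportion. All of this stands, and it is why the scoring should not change. It does not make the completion wording something the score can show.

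A reader might infer more than the documents support:

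- **That the plan ignores the dog.** It does not. Responses are noted and the summative evaluations are video-recorded. They are simply not counted.
- **That the result cannot support Hypothesis 1 at all.** It can support the competence part. Only the dog-completion part is left without data.
- **That a participant could score 2 on every skill while the dog performs none, so that any total is compatible with anything from 0 to 5 completed skills.** This cannot be checked, because the blank adapted form is not in the text available here. It also sits badly with the Aim 1 Rationale, where timing means marking the behavior the moment it happens. If the dog never performs, there is no completed behavior to mark. Handler score and dog response are probably related; how closely is unknown.

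**Conclusion.** The point holds for the dog-completion part of Hypothesis 1 and for the matching wording in the expected results. As planned, Aim 1 can conclude on handler competence. It cannot conclude that dogs completed at least 4 of 5 skills, because no analysis counts that and no evidence links the two.

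The size of the gap cannot be estimated from the documents. The range in the working, from 0.98 down to 0.19 for a handler competent on all five skills, rests on an assumed response rate and independence between skills. It shows only that equivalence needs a rate near 1. The mismatch between the 5/10 total and the 4-of-5 rule needs no assumption: 40 score patterns meet the total without four competent skills, and 5 do the reverse.

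**What to change.** 1. **Align the wording.** State Hypothesis 1, the expected result and the primary outcome as handler competence, meaning a summative PPAHE score of 1 or higher on at least 4 of 5 skills. Use this to define successful completion of training, which the analysis text does not define explicitly. Replace the 5/10 benchmark or reconcile it with this rule. This is more than an edit: a participant scoring 1,1,1,1,0 meets the new rule and misses 5/10, while one scoring 2,2,1,0,0 does the reverse. The change should be dated and made without reference to summative scores.

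2. **Count what is already noted.** At the summative evaluations, code the dog's response as yes or no per skill (performed on cue). Beside the handler-competence proportion, report descriptively the proportion of participants whose dog performed at least 4 of 5. This would also give the first evidence on the equivalence the plan now assumes.

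**Cost.** A protocol text change and a little extra coding, which could probably be done from the existing video. The dog figure may be less favorable than the handler figure. It will partly reflect the dog's prior training or an unfamiliar shelter dog, so it should stay descriptive.

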### Preliminary Data:

The training procedures and lesson plans have been validated through use with four individuals with post-stroke aphasia (one with right-sided hemiplegia) who completed training and immediate post-treatment evaluation. Three participants worked with a family dog and the fourth participated in the program at the PSPCA. Consistent with our hypothesis, on program completion all four participants demonstrated ability to cue their dog(s) to perform a minimum of four out of five obedience skills commensurate with a handler skill level at or above a '1' on the *PPAHE*.

**Specific Aim 2: Define participant characteristics associated with recruitment, retention, compliance and program acceptability/satisfaction relevant for determining PATD candidacy.** *Hypothesis 2:* PWA will demonstrate high (above 80%) retention and compliance rates, and high program satisfaction, including increases in self-reported ratings of psychosocial well-being. To test this hypothesis, our primary outcome measure will be the *Assessment of Living with Aphasia* (Kagan et al., 2010), complemented by self-report of participants' PATD experience gathered through an ALA-modeled qualitative spoken interview and a written, aphasia-friendly, satisfaction survey.

**Rationale:** Our second hypothesis is supported by a growing literature regarding the physiological and psychosocial benefits of human-dog interaction (Friedmann & Son, 2009; Lundqvist et al., 2017; Odendaal & Meintjes, 2003) and the likely mechanisms of action for AAT, which include as Beetz (2017) described, "promoting the preconditions of learning" (p. 7) by increasing intrinsic motivation, attention, and positive mood and decreasing fear and stress (Beetz, 2017; Blakemore & Frith, 2005; Wholfarth et al., 2013). The direct and

Assessing an animal-assisted treatment program for adults with aphasia:  
the Persons with Aphasia Training Dogs (PATD) Program

regular interaction with dogs provided in the PATD program also provides for 'active engagement' with the animal, which may support greater potential for deriving these benefits than simply having the dog present (Dietz et al., 2012).

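### A summative score of 5/10 is not equivalent to competence on 4 of 5 skills, and the primary-analysis sentences do not say which criterion defines success

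*Combined protocol and SAP*

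**What the plan says.** Hypothesis 1 (Approach, Specific Aim 1) is that, when the program ends, "PWA will be competent in using positive reinforcement techniques, to independently cue a dog to complete a minimum of 4 (of 5") trained skills, assessed with the adapted PPAHE. Each skill is scored 0, 1 or 2. For the weekly probes, Statistical Considerations under Specific Aim 1 says the scores "will be dichotomized as competent (1 or 2) vs. not competent (0"). The summative score is a total from 0 to 10.

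The same section then links the total to the hypothesis: "a score of 5/10 points corresponds with achieving a minimum of a 1" "on all five targeted obedience behaviors or achieving a 2" "on at least one behavior and 1 on three others". The next sentence gives the primary analysis: "the proportion of subjects that successfully completed the training will be quantified", with a two-sided 90% exact binomial interval. Statistical Design and Power repeats that analysis but contains neither the 4-of-5 criterion nor the 5/10 sentence.

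Expected results first states the 4-of-5 expectation, then adds: "It is also expected that the median cumulative score will be at least 5", with the same two-pattern explanation. Preliminary Data reports that all four pilot participants could cue "a minimum of four out of five obedience skills commensurate with a handler skill level at or above" 1.

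**The concern.** The plan offers a total of 5 as the score counterpart of competence on four skills. A total does not record how many skills contributed to it: high scores on a few skills can offset zeros on others, and four scores of 1 reach only 4. The correspondence therefore fails in both directions.

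Two things are at stake. First, a reader of the results could take a median of 5 or more as showing competence on four skills, which it does not. Second, the 5/10 sentence stands directly before a primary proportion whose success criterion is not restated. Two analysts could classify the same participant differently. With 20 participants, each reclassification moves the primary estimate by 1/20 = 0.05.

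**Working it through.** **Inputs.** Five skills, each scored 0, 1 or 2; total 0 to 10; hypothesis of at least 4 of 5 skills; a competent score is 1 or 2 (all from Specific Aim 1). Let k be the number of skills scored 1 or 2. There are 3^5 = 243 possible score patterns.

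**The plan's own patterns.** 1+1+1+1+1 = 5 and 2+1+1+1+0 = 5. Both total 5 and both have k of at least 4, so what the sentence names is correct as far as it goes.

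**All patterns totalling exactly 5.**

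| Type | Count | k |
|---|---|---|
| 1,1,1,1,1 | 1 | 5 |
| 2,1,1,1,0 | 5!/(1!·3!·1!) = 20 | 4 |
| 2,2,1,0,0 | 5!/(2!·1!·2!) = 30 | 3 |

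The sum is 51. The plan leaves out the third type, which is 30 of the 51 and has only three competent skills.

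**4 of 5 against a total of 5 or more.**
- k = 5: 2^5 = 32 patterns. k = 4: 5 × 2^4 = 80. So 32 + 80 = 112 patterns meet 4 of 5.
- Of the 80 with k = 4, five are 1,1,1,1,0, which total 4. The other 75 include at least one 2 and total 5 or more.
- The plan's two patterns, read as minimums, cover 32 + 75 = 107 patterns. All 107 meet 4 of 5 and all total at least 5.
- With k = 3, the total reaches 5 only if at least two of the three skills score 2: 30 of type 2,2,1,0,0 and 5!/(3!·2!) = 10 of type 2,2,2,0,0 (total 6), so 40. With k of 2 or less the total cannot exceed 4.
- Total of 5 or more: 107 + 40 = 147. Disagreement with 4 of 5: 40 + 5 = 45 of 243.

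**Other cut-offs.** The lowest total that meets 4 of 5 is 4 (1,1,1,1,0) and the highest that fails it is 6 (2,2,2,0,0), so no cut-off separates them.

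| Total at least | Passes but k < 4 | Fails but k ≥ 4 |
|---|---|---|
| 4 | 80 | 0 |
| 5 | 40 | 5 |
| 6 | 10 | 26 |
| 7 | 0 | 61 |

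**Illustration in probabilities (assumed).** The documents give no score distribution. Assume independent skills, with q the chance of a 1 or 2 on a skill and r the share of those scored 2. Then

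P(k ≥ 4) = q^5 + 5q^4(1−q)

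P(total ≥ 5) − P(k ≥ 4) = 10q^3(1−q)^2[3r^2(1−r) + r^3] − 5q^4(1−q)(1−r)^4

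| q | r | P(total ≥ 5) | P(k ≥ 4) | Difference |
|---|---|---|---|---|
| 0.6 | 0.75 | 0.628 | 0.337 | +0.291 |
| 0.8 | 0.50 | 0.814 | 0.737 | +0.077 |
| 0.9 | 0.50 | 0.934 | 0.919 | +0.016 |
| 0.8 | 0.25 | 0.640 | 0.737 | −0.098 |

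For the first row: 10 × 0.216 × 0.16 × 0.84375 = 0.2916, less 5 × 0.1296 × 0.4 × 0.0039 = 0.0010, gives 0.291. Over q from 0.6 to 0.9 and r from 0.25 to 0.75, the difference runs from about −0.10 to +0.29.

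**Effect of one participant.** 16/20 has a 90% exact interval of 0.599 to 0.929; 15/20 has 0.544 to 0.896.

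**The case against.** The strongest reply is that the intended criterion is clear. Hypothesis 1 says 4 of 5 at the end of the program and names the adapted PPAHE as its test. Statistical Considerations restates 4 of 5 just before the primary analysis, and the pilot was judged on 4 of 5 at level 1 or above. That stands: a reader might infer that the plan contains no success rule at all, and these places do not support that. What remains is narrower. Neither sentence giving the primary analysis names the criterion, Statistical Design and Power omits it altogether, and the sentence offered as its score equivalent does not match it.

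Three other inferences also go too far.
- **That 5/10 is the pass mark for the primary proportion.** The plan never says so; it only describes what that total corresponds to.
- **That leaving out 1,1,1,1,0 is an arithmetic error.** That pattern totals 4, so it does not belong in a list of ways to score 5. It is a mismatch with the hypothesis, and matters only if the sentence is taken as describing every way of meeting 4 of 5.
- **That the median is the plan's test of Hypothesis 1.** Expected results gives the 4-of-5 expectation separately and the median is secondary. Only the clause that equates a total of 5 with the two patterns is wrong.

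It is also fair to say that the largest gap in the illustration is a corner of an assumed grid. The gap is small when competence is high and 2s are common, and it changes sign when few 2s are given. All four pilot participants met 4 of 5, which, though very little evidence, lends no support to the low-competence corner. Finally, the adapted PPAHE form is in an appendix that was not available, so a pass rule printed on it cannot be excluded. Such a rule would still not correct the 5/10 statement.

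**Conclusion.** The concern holds in this form. A total of 5/10 is not equivalent to competence on 4 of 5 skills, in either direction, and no cut-off on the total is. The arithmetic is certain given five skills scored 0 to 2: 45 of 243 patterns are discordant, 40 passing on the total with three competent skills and 5 failing on the total with four. These counts say nothing about how often such patterns will occur. The range of about −0.10 to +0.29 in the success proportion depends wholly on the assumed independence and on the assumed ranges of q and r.

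The success criterion for the primary proportion is best read as 4 of 5 at level 1 or above at the end of training, but the analysis sentences should say so. A reader might infer that the trial could reach a wrong decision through this. The documents do not support that: the primary analysis is an estimate with an interval, with no go/no-go threshold. The harm is an ambiguous primary proportion or a misread median.

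**What to change.** 1. In Specific Aim 1, Statistical Considerations, and in Statistical Design and Power, define primary success as a score of 1 or 2 on at least 4 of the 5 skills at the end-of-training summative PPAHE. Say that 1,1,1,1,0 counts as a success, as it would have in the pilot; the investigators should confirm this is their intent.
2. Delete the 5/10 correspondence in Statistical Considerations and Expected results, or correct it by stating that 5 can also arise with three competent skills and that four scores of 1 total 4.
3. Keep the 0 to 10 total and its median as a secondary descriptive summary, and state that it is not read as evidence of 4 of 5.
4. Check that the adapted PPAHE form carries no conflicting pass rule.

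The cost is wording only. The total is built from the five skill scores, so no new data, visits or participants are needed.

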**Version Date: October 28, 2024**

**Principal Investigator: [name] CCC-SLP**

## PROTOCOL SYNOPSIS

This study is an investigation of the feasibility of administering, and quantifying the effects of a canine-assisted aphasia treatment entitled, the Persons with Aphasia Training Dogs Program. Individuals with aphasia are trained in using positive reinforcement techniques to train dogs in basic obedience skills. On program completion, participants are evaluated on their ability to use the techniques and are assessed for the effects of program participation on psychosocial aspects of living with aphasia and on cognitive-linguistic factors. It is hypothesized that 1) persons with aphasia will be able to independently cue a dog to perform basic obedience skills and that 2) participants will demonstrate increases in self-confidence and social engagement.

Participants self-select into groups based on interest and dog-status: a) PATD participants working with family dog or b) PATD participants working with PSPCA (Pennsylvania Society for the Prevention of Cruelty to Animals) shelter dogs. Guidance is provided relative to the fact that some interested participants may have a family dog that is not eligible to participate (e.g., bite history), in which case the participant would be invited to participate with PSPCA dogs. All PATD and behavioral assessment sessions are conducted individually, i.e., between an individual participant and members of the study team.

The program was previously run as an activity offered by the MossRehab Aphasia Center. The current study will enroll a minimum of 20 PATD participants and is informed by the PI's experience of administering the program and commensurate to the timeline and resources of the funding mechanism. For this feasibility study, data analysis will be performed using criterion-referenced benchmarks to assess within- subject effects and, for secondary analyses between-group (immediate vs. waitlist) differences where possible.

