### Statistical Design and Power

For this feasibility study, we anticipate enrolling a minimum of twenty participants with stroke-aphasia.

Scores from weekly probes will allow for analysis of change in level of 'competence' over time, as determined using the *PPAHE* for that skill. For the purpose of statistical analyses of weekly evaluations, three scores (0="not ready", 1="ok", 2="best") will be dichotomized as competent (1 or 2) vs. not competent (0). In addition to the weekly evaluations, at the end of the training period, each participant will receive a summative score on the adapted *PPAHE*. This score may range from 0 to 10. For the primary analysis, the proportion of subjects that successfully completed the training will be quantified with the corresponding two-sided 90% exact binomial confidence interval. For the secondary analysis, (i) the median cumulative score will be computed with the corresponding two-sided 90% distribution-free confidence interval (Hahn & Meeker, 2011) and (ii) the weekly competence scores will be analyzed using the repeated measures logistic regression model. With the total sample size of 20 subjects, the width of the two-sided 90% exact binomial confidence interval is at most 0.38 if the observed proportion of subjects successfully completed the training is 0.5. The interval is narrower if the observed proportion of successes is higher (or lower) than 0.5.

The mean pre-to-post-training change in each ALA domain scores will be computed with the corresponding 90% confidence interval. With the total sample size of 20 subjects, the width of the two-sided 90% confidence interval is equal to 0.39 standard deviations of the pre-to-post-training changes. For the secondary analysis, we will evaluate the mean difference in each ALA domain scores between the immediate and delayed treatment arms at week 7 using the two-sided 90% confidence interval and two-sided two-sample t-test with alpha 0.1 (reflective of the small size pilot study). The results of comparison between the immediate and delayed treatment arms will be used to inform future larger studies. Qualitative data derived from narratives produced by PWA during administration of the PATD ALA-supplement will be orthographically-transcribed for offline analysis of themes discussed consistent with procedures detailed by Luck & Rose, 2007.

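### The Aim 1 precision statement is slightly too favourable: with 20 subjects the 90% exact binomial interval reaches a width of 0.396 (0.40), not 0.38

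*Combined protocol and SAP*

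**What the plan says.** The primary analysis for Specific Aim 1 is descriptive: "the proportion of subjects that successfully completed the training will be quantified with the corresponding two-sided 90% exact binomial confidence interval". Its precision is given under Statistical Considerations for Aim 1 and repeated word for word under Statistical Design and Power: with 20 subjects, "the width of the two-sided 90% exact binomial confidence interval is at most 0.38 if the observed proportion", the condition in full being "if the observed proportion of subjects successfully completed the training is 0.5". Both places then add: "The interval is narrower if the observed proportion of successes is higher (or lower) than 0.5". Neither says which exact interval is meant.

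The Protocol Synopsis does not derive the sample size from this width. It rests the number on the investigator's earlier experience of running the program and on its being "commensurate to the timeline and resources of the funding mechanism". Twenty is a floor: "we anticipate enrolling a minimum of twenty participants with stroke-aphasia".

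**The concern.** The inputs to the width are all stated: 20 subjects, 10 successes, 90% confidence, two-sided, exact. The result can therefore be recomputed directly, and the standard exact method gives a larger value than the plan does. Because the plan words its figure as an upper bound, a larger true value makes the sentence false and cannot be treated as a loose approximation.

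This is the only quantitative precision statement for the Aim 1 primary analysis, and it errs in the favourable direction. What is at stake is how accurately the study describes its own precision, not its design.

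**Working it through.** **Inputs.** From Statistical Considerations (Aim 1) and Statistical Design and Power: n = 20, observed proportion 0.5 (so x = 10), 90% two-sided (5% in each tail), exact binomial. Stated width: at most 0.38.

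**Step 1. Try to reproduce 0.38.** The Clopper-Pearson limits are beta quantiles:

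- lower limit = the 0.05 quantile of Beta(x, n − x + 1) = Beta(10, 11) = 0.3020
- upper limit = the 0.95 quantile of Beta(x + 1, n − x) = Beta(11, 10) = 0.6980
- width = 0.3961 from unrounded limits, which rounds to 0.40

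The stated 0.38 is not reproduced.

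**Step 2. Check by tail probability.** At the lower limit, P(X ≥ 10 | n = 20, p) must equal 0.05. At p = 0.302 it is 0.050. A symmetric interval of width 0.38 around 0.5 would start at 0.5 − 0.19 = 0.31, where the tail probability is 0.059. That exceeds the 5% allowed.

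**Step 3. Is 10/20 the widest case?** Clopper-Pearson widths at n = 20:

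| Successes | Width |
|---|---|
| 10 | 0.396 |
| 9 or 11 | 0.394 |
| 8 or 12 | 0.389 |
| 7 or 13 | 0.381 |
| 6 or 14 | 0.368 |
| 5 or 15 | 0.352 |

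The maximum is at 10, so the plan's sentence about narrowing is right for this method. At two decimals the bound of 0.38 is exceeded for 8 to 12 successes. At 7 and 13 the width (0.3807) rounds to 0.38.

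**Step 4. Could another exact interval be meant?** Two were obtained by numerical inversion (grid step 0.0001):

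| Method | Width at 10/20 | Width at 8/20 and 12/20 |
|---|---|---|
| Clopper-Pearson | 0.396 | 0.389 |
| Blaker | 0.356 | 0.382 |
| Sterne | 0.350 | 0.378 |

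Blaker and Sterne meet the bound at 10/20, but both are wider at 8 and 12 successes than at 10. The plan says the opposite. Clopper-Pearson fits the statement about narrowing and misses the figure. None of the three fits both sentences.

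**Step 5. Could a non-exact method explain the figure?** At 10/20: Wald 0.368, Wilson 0.345, Jeffreys 0.352, mid-P 0.360, Wilson with continuity correction 0.389, Wald with continuity correction 0.418. None gives 0.38, and none is the exact method that the plan specifies.

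**Step 6. Which sample size would give 0.38?** The largest Clopper-Pearson width is 0.406 at n = 19, 0.396 at n = 20, 0.386 at n = 21 and 0.377 at n = 22. The stated bound is first met at 22 subjects.

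**Size of the discrepancy.** 0.396 − 0.38 = 0.016 in full width, or 0.008 in half-width. 0.016 / 0.38 is about 4%.

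**The case against.** The strongest objection is that the plan says exact binomial and never says Clopper-Pearson. Under Blaker or Sterne the statement about 10/20 is literally true, and the faulty sentence would be the one about narrowing. This stands as a caveat: the sponsor should confirm the method. It does not rescue the text, because one of the two sentences is wrong under each of these methods. Clopper-Pearson is what an unqualified exact binomial interval ordinarily means, and it is the only one of the three consistent with the narrowing sentence.

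A second objection is that the error lies where the trial does not expect to be. The plan anticipates that participants will succeed, and all four pilot participants met the criterion. At 14 or more successes the width is 0.368 or less, already inside the stated bound. This is correct and limits the practical effect, but the sentence is explicitly about the case of 0.5.

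A third is that twenty is a minimum, and two more participants would bring the maximum to 0.377. That is also true, but the sentence is conditioned on a total of 20. Losses would move the width the other way, to 0.406 with 19 evaluable subjects.

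**Conclusion.** The concern holds. Taking the interval as Clopper-Pearson, the maximum 90% width with 20 subjects is 0.396, and the stated 0.38 is not a rounding of it. If the sponsor intended Blaker or Sterne instead, the narrowing sentence would be the one to correct.

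The point is minor. The overstatement of precision is 0.016 in full width. The sample size was not derived from it, no success criterion depends on it, and neither the planned analysis nor its conclusions change.

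**What to change.** Under Statistical Considerations for Aim 1 and under Statistical Design and Power, change the bound from 0.38 to 0.40 and name the method, for example: at most 0.40 (Clopper-Pearson, 0.302 to 0.698 at 10/20). The sentence that follows can stay, since it is correct for Clopper-Pearson. The sponsor should confirm that this is the interval to be reported, so that the analysis matches the text.

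The cost is one phrase in each of two places and a slightly less favourable stated figure. Nothing else needs to change.
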